1.1 Introduction

Hospital personnel continually survey the infectious and mechanical complication rates related to short-term Central Venous Access Devices (CVADs). Routine reporting to hospital administration and/or government agencies has become mandatory in many countries, since these CVAD complications can significantly impact patient outcomes and healthcare costs. However, routine or mandatory surveillance (audits) of short peripheral IV catheter (PIVC) therapy does not occur in hospitals globally, despite the recognized impact of PIVC failure. PIVC failure is defined as any premature removal of an PIVC before the end of treatment, other than for routine replacement (includes phlebitis, infiltration, occlusion, accidental removal, leaking, dislodgement and local or catheter-related bloodstream infection^{2,12}).

PIVC therapy is beneficial to patients requiring medications or fluids that can be administered using peripheral veins and these catheters: (1) are used considerably more often than the CVADs, (2) have an overall failure rate that lies between 35% and 50%^{2, 3, 4, 5} and (3) can lead to bloodstream infections, which are less frequent than those associated with CVADs but are still serious complications⁶. Moreover, the rates of these and other complications that are known to contribute to PIVC failure, such as phlebitis and infiltration, are under-reported⁸. Understanding the impact of PIVC-related complications is paramount, given that PIVC failures can lead to delays in IV therapy, increased length of hospital stays and higher hospitalization costs⁷.

According to Alexandrou *et al.* (2015)⁸, there are currently little data on PIVC management practices across different regions of the world, making it difficult to identify contributing factors for PIVC failure in general and for PIVC-related complications in particular. One of the main issues arising as a consequence of inadequate PIVC management practices is catheter dislodgment. Patients having securement-related issues, which might be associated with poor dressing and/or securement devices, are at greater risk for infection, thrombus formation and air embolism and are likely candidates for catheter replacement.

Therefore, though evidence-based strategies have been developed to reduce PIVC-related complications, it is not known whether these strategies are consistently applied in the acute care setting⁶. Audits and benchmarking of practice are necessary to drive improvement strategies and incite the development of interventional studies.

A prevalence study is a quick method to audit and measure PIVC-related complications and compliance to evidence-based strategies. The Infusion Therapy Standards of Practice (2016) recommend regular evaluations of adverse events associated with PIVC use, such as infiltration, phlebitis, and/or bloodstream infection in populations of interest. Incidence studies, point prevalence studies and analyses of International Classification of Diseases (ICD) codes documented in electronic medical records are types of studies that can be used to meet this purpose. These regular evaluations must: (1) use consistent definitions; (2) compare current failure rates to internal historical data, to identify areas of improvement; and (3) result in data that are provided to the institution's leadership.

In this national, multicenter, cross-sectional study, healthcare professionals working in acute care hospitals, with expertise in PIVC therapy, will audit patient medical records and directly observe PIVC insertion sites on select hospital wards. The prevalence of PIVC-related complications that are identified upon observation will be determined. Furthermore, a

summary of PIVC management practices at each participating hospital or ward will be obtained.

1.2 Risk/Benefit Summary

Risks to implementing this study are minimal. It is an observational study, centered on the study of PIVCs indwelling in adult patients admitted in acute care hospitals in Brazil, but not on the patients themselves.

Products used in PIVC therapy have some benefit in maintaining the PIVC's location and patency while the needed medical therapy is infused via the catheter. Yet, these benefits are sometimes overshadowed by several potential risks. The risks of implementing PIVC therapy include, but are not limited to: phlebitis, infiltration, extravasation, skin injury, ecchymosis or hematomas, local infection at the insertion site, catheter-related blood stream infections (CRBSI), catheter dislodgement, deep venous thrombosis, excessive blood loss from a disconnected infusion system, among others.^{10,11}

These risks or complications might be influenced by: (1) the adhesive and catheter stabilizing properties of the dressing cover and/or tape; (2) the ability of the nurse to visualize the site for early detection of complications; (3) the effectiveness and duration of the skin's antimicrobial preparation; (4) the aseptic insertion technique and site location of the PIVC; (5) the design and gauge of the PIVC; (6) the medicinal or fluid therapy infused through the catheter; and (7) patient-related factors, e.g. gender, activity, skin condition, co-morbidities and history of previous PIVC complications.^{4,7,10,11}

When products for PIVC therapy are effective, properly used and accompanied by good clinical practice, the benefits of PIVC therapy will significantly outweigh the risks identified above. The products that will be under observation during this study are all approved by the Brazilian regulatory agencies and are currently used at the hospitals for PIVC therapy. If the products are used as intended, the benefit obtained with the use of these medical devices should outweigh the risks associated with each one.

It is expected that the prevalence study data will contribute to the site's quality improvement program and help drive the nurses to: (1) evaluate and procure products to reduce complications; (2) develop and implement training programs on evidence-based strategies and (3) continue a surveillance practice to determine if new or modified interventions for PIVC management impact patient outcomes over time⁷. Furthermore, this study can provide a foundation for a wider point prevalence study of PIVC-related complications in Brazil and/or to design and implement further clinical studies of PIVC management.

The Sponsor plans to use the data (de-identified) of this study for the pre-interventional phase of a pre-post interventional study. The data are to be compared to prevalence data obtained after the introduction of a dressing, which would comprise the post-interventional phase of the abovementioned pre-post interventional study.

All necessary measures will be implemented to ensure the confidentiality of the research participants' data. However, a minimal risk of data confidentiality breaches cannot be entirely ruled out.

1.3 Investigational Material Application

No investigational materials will be provided or used in this prevalence study. All PIVC-related products used at or on the PIVC insertion sites by the participating hospitals are approved by the Brazilian regulatory agencies, routinely purchased by the hospital and available to the physicians and nurses at the time of the study. Characteristics of the products

used at the PIVC insertion sites observed during the study will be documented. All PIVC brands will be observed in the context of this study.

1.4 GCP and Regulatory Requirements

The whole conduction of the study will be performed in compliance with the protocol, the principles laid down on the Declaration of Helsinki, ICH's Good Clinical Practice (GCP) and all applicable regulatory requirements.

This research project was prepared in accordance with Resolution No. 466 of December 12, 2012 of the National Health Council, which establishes the ethical standards for research involving human beings. Data collection will occur only after approval of the study and its documents by the Ethics Committee of each research center.

1.5 Study Population

All persons with 18 or more years of age, admitted to the participating facility and who meet the eligibility criteria in Section 4.

2. Study Objectives and Purpose

2.1 Primary Objective

- To determine the prevalence of any PIVC-related complications, clinical **or** mechanical, in acute care hospitals in Brazil.

2.2 Secondary Objectives

- To determine the prevalence of simultaneous clinical **and** mechanical PIVC-related complications in acute care hospitals in Brazil.
- To determine the prevalence of PIVC-related clinical complications, overall and by type, in acute care hospitals in Brazil.
- To determine the prevalence of PIVC-related mechanical complications, overall and by type, in acute care hospitals in Brazil.
- To determine the prevalence of PIVC-related quality issues, overall and by type, in acute care hospitals in Brazil.
- To describe the standards of practice for PIVC management employed in acute care hospitals in Brazil.

2.3 Exploratory Objectives

- To explore the association between PIVC-related complications and subjects' socio-demographic characteristics, and other baseline characteristics.

3. Study Design

3.1 Study Type

This will be a national, multicenter, cross-sectional study to assess the prevalence of PIVC-related complications in Brazil. Estimates of the prevalence of clinical and mechanical complications, as well as quality issues associated with PIVC management, will be studied. Moreover, hospital- or ward-specific standards of practice for PIVC management will be described. The study will be considered the pre-study stage of a pre-post interventional study. The de-identified data from this study will be used to calculate the effect of the intervention on the PIVC complication rate.

3.2 Study Setting

The study is expected to be conducted at three acute care centers located in Brazil. Assessment of PIVCs insertion sites and related complications, as well as of standards of practice for PVIC management, will take place at the hospitals' general or specialty admission wards. Wards where the study procedures are not to be carried out include outpatient clinics, mental health wards, emergency wards and burn units.

3.3 Study Procedures

[figure not shown]

Figure 1– Flowchart of study activities

All of the study team will receive training on the study protocol and other protocol-related procedures prior to study start. At each center, the study will only start after the study protocol and PIVC site assessment training is completed (Figure 1).

Study procedures will be completed in a single center (pilot study site) prior to initiating study activities in the remaining centers. This strategy will allow for the adjustment of any training or monitoring needs identified at the first center. At each study site, including the pilot study site, study activities at the participating wards will be performed in parallel. The Principal Investigator (PI) will be responsible for selecting, at each site:

- The wards that will be audited within the context of this study.
- The healthcare professionals (auditors) that will be responsible for auditing the participating wards. Auditors will be healthcare professionals (e.g. nurse, resident physicians) with extensive experience in PIVC therapy and who are employed by the study site.

Once the PI has selected the hospital's wards that will be participating in the study, the PIVC Therapy Standards of Practice Questionnaire will be completed by him/her or a designee. If there are individual PIVC therapy standards of practice per ward, rather than hospital-wide standards, the PI will interview the ward nurse manager or a ward clinician of the selected wards and complete the PIVC Therapy Standards of Practice Questionnaire for each ward.

To minimize subject selection bias, all subjects will be identified and invited to participate in the study consecutively, as the auditor goes through the ward. An informed consent process will be carried out by the PI, auditor or a designee. After the subject provides his/her written informed consent to participate in the study, data will be collected from the subject's medical records and by observation of the PIVC site. All PIVC sites, regardless of catheter commercial brand, should be assessed. Data on each PIVC site will be recorded on the Individual PIVC Questionnaire.

In addition to collecting general characterization data on the patient and the PIVC, the auditor will be observing the PIVC site for presence of the following complications (see Appendix I for definitions):

- Clinical complications:
 - Phlebitis:
 - According to grade: grade 1-4
 - According to etiology: mechanical, chemical, infective
 - Hematoma
 - Ecchymosis
 - Skin injury
 - Local infection
- Mechanical complications:
 - Catheter dislodgement
 - Occlusion
 - Extravasation
 - Infiltration (grade 1-4)
 - Leaking at the insertion site

The PIVC will also be evaluated for the presence of the following quality issues:

- Unstable PIVC
- Blood reflux
- Uncontrolled IV infusion rate
- Site dressing partially detached
- Site dressing totally detached (site exposed to environment)

- Medical tape added to dressing edges
- Unclean dressing
- Discomfort at site with or without palpation
- Uncovered tubing access port
- Lack of visibility at the PIVC site

If the patient has more than one PIVC, one questionnaire will be completed for each PIVC.

Once the wards' audits are concluded, the study-specific electronic case report forms (eCRFs) will be completed by the PI or study designee. The sponsor or sponsor's representative will perform the monitoring activities and, based on the number or type of inconsistencies/ queries raised, the monitor may deem that the site requires additional training. Once the additional training is complete, the audit process will continue with any changes deemed necessary by the monitor to improve the quality and quantity of data collected.

The process of PIVC-related data collection will be repeated at each study site until at least 100 PIVCs have been audited (Table 1).

Table 1 - Study data collection and procedures per audited ward

Study procedures ^a	Pre-audit	Audit day
Completion of hospital's or ward's current PIVC Therapy Standards of Practice Questionnaire ^b	X	
Inclusion and exclusion criteria review		X
Informed consent form signature		X
Completion of Individual PIVC Questionnaires		X

a. Procedures and timeline to be repeated if more than one ward is to be audited at the study site.

b. Repeat survey of current PIVC standards of practice, if the standards are ward-specific.

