3.4 Study Data Sources

Information on the hospital's or ward's standards of practice for PIVC management will be recorded by the PI or designee into the Hospital/Ward PIVC Therapy Standards of Practice Questionnaire.

After the subject provides his/her written informed consent, subject and PIVC-related data will be collected from the subject's medical records and by observation of the PIVC insertion site. This information will be recorded into the Individual PIVC Questionnaire.

The investigator will be responsible for ensuring that all the required data is collected in the study-specific eCRF. No subject identifiable information will be captured.

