3.5 Randomization and Blinding

No blinding will occur during the study. As this is an observational study of existing PIVC practice and related complications, randomization is not applicable.

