3.7 Study Duration

The study is expected to be open at each participating site until a minimum of 100 PIVC sites are assessed, so that a minimum of 300 PIVCs are assessed at all three participating hospitals.

Since this is an observational, cross-sectional study, each patient's involvement in the study will have a duration of one day only.

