5.2 Anticipated Device-Related Adverse Events

This is an observational, cross-sectional study that is not designed to identify or quantify a safety hazard relating to an authorized medicinal product or medical device. Nevertheless, there are anticipated device-related adverse events that may occur during this study and are related to the current practice of PIVC therapy at the study sites. According to IV professionals and IV-related literature, the anticipated device-related adverse events that may occur are:

1. Certain skin reactions, such as mild to moderate redness, blisters, itching, and/or minor skin denudations at the site of the adhesive which should dissipate within one to seven days after removal;
2. Loss of the PIVC from the insertion site;
3. Leaking of fluid or blood from PIVC insertion site;
4. Phlebitis and/or;
5. Infiltration of an infusate.

5.3 Unanticipated/Serious Device Related Adverse Events:

The following list of unanticipated and/or more serious device-related adverse events are unlikely to be identified during this study, unless the audit nurse reads of the event during the medical record review. Excluding the severe skin reactions, the nurse auditors will most likely not be aware of the following unanticipated and/or serious adverse events:

1. Any catheter-related phlebitis with a fever;
2. A catheter-related phlebitis or infiltration that extends hospitalization;
3. A catheter-related blood stream infection (PIV-CRBSI);
4. Severe skin stripping or skin reaction; or
5. Extravasation.

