6.2.4 Exploratory endpoint analyses

Exploratory analyses will be performed with the aim of identifying the subject- and PIVC characteristics associated with the occurrence of PIVC-related complications.

The association of qualitative variables with the occurrence of PIVC-related complications will be performed with the chi-squared test or with the Fisher's test, while the association of quantitative variables with the occurrence of PIVC-related complications will be performed with the student's t test or the Mann-Whitney test.

Generalized estimating equation (GEEs) models will be used to identify the most important patient characteristics associated with the multivariate binary occurrence of PIVC-related complications, with a Logit link function and considering the correlation structure assumed as exchangeable within patients. The Odds Ratios as well as 95% confidence intervals will be estimated. The significance level will be established at 5%.

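### Section 3.3 has the auditor gather PIVC characteristics, partly from the chart, and judge complications on the same day with no order set, so chart knowledge can bias the exploratory associations in 6.2.4

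*Combined protocol and SAP*

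**What the plan says.** Section 3.3 names two sources for each PIVC: "data will be collected from the subject's medical records and by observation of the PIVC site". It gives both tasks to the auditor: "In addition to collecting general characterization data on the patient and the PIVC, the auditor will be observing the PIVC site for presence" of the listed complications. Section 3.4 sends both kinds of data to one form: "This information will be recorded into the Individual PIVC Questionnaire". Table 1 places that form on the audit day, and Section 3.7 adds that "each patient's involvement in the study will have a duration of one day only". Section 5.3 indicates that the auditor is the person who reads the chart, since certain events will go unnoticed "unless the audit nurse reads of the event during the medical record review". Section 3.5 states: "No blinding will occur during the study".

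Section 3.4.1 lists what the auditor may learn from the chart or the site: insertion date and time (hence dwell), who inserted the catheter and where, drugs and fluids of the past 24 hours, whether the site is overdue for relocation, and whether a site assessment was charted in the past 24 hours.

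On the outcome side, Section 1.1 says: "The prevalence of PIVC-related complications that are identified upon observation will be determined". Section 6.2.4 aims at "identifying the subject- and PIVC characteristics associated with the occurrence of PIVC-related complications", and Section 6.2.1 sets a 5% significance level for those tests. The visible text does not require the site to be scored before the chart is opened, and it does not provide for a second rater or an agreement check.

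**The concern.** Several complications rest on soft thresholds. In Appendix I the lowest phlebitis grade needs only erythema, with or without pain, and local infection can be called on redness or induration near the exit site. One such call puts a PIVC in the primary numerator.

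If the auditor already knows that a catheter has been in for a long time, has carried an irritant drug or was noted as red the day before, a doubtful site may be called positive more readily. A doubtful site without those features may be passed. The error in the outcome then depends on the exposure. Such differential misclassification can produce an association in 6.2.4 where none exists, or distort a real one. It arises with any auditor, including one from outside the ward, because it comes from what the auditor knows when making the call.

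**Working it through.** The plan gives no figure to reproduce. It contains no sensitivity, specificity or agreement value, and Section 6.3 states that no formal sample size calculation was done. What follows is an illustration on assumed values.

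**Inputs**
- From the plan: 300 PIVCs in total (Section 6.3); 5% significance level (Section 6.2.1).
- Assumed: true prevalence p = 0.35 in both groups; a charted factor present in half the PIVCs (150 and 150); two-sided tests; clustering ignored. The 35% to 50% in Section 1.1 is a catheter failure rate, not a complication prevalence, so it does not supply p.
- Assumed: error d = 0.05 or 0.10.

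**Model A, error in both directions.** A fraction d of true negatives is called positive in exposed sites, and a fraction d of true positives is missed in unexposed sites.
- Exposed: p + (1 − p)d. Unexposed: p(1 − d).
- d = 0.05: 0.35 + 0.65 × 0.05 = 0.3825, and 0.35 × 0.95 = 0.3325. OR = (0.3825/0.6175) / (0.3325/0.6675) = 1.24.
- d = 0.10: 0.415 and 0.315. OR = (0.415/0.585) / (0.315/0.685) = 1.54.

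**Model B, over-calling in exposed sites only.** Unexposed sites stay at 0.35.
- d = 0.05: 0.3825 against 0.35, OR = 1.15.
- d = 0.10: 0.415 against 0.35, OR = 1.32.

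**Chance of p < 0.05 with no true association** (normal approximation, 150 per group): z = difference / √[(p₁(1 − p₁) + p₂(1 − p₂))/150], and the chance is about Φ(z − 1.96).

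| Model | d | Observed, exposed / unexposed | OR | Chance of p < 0.05 | Overall prevalence |
|---|---|---|---|---|---|
| A | 0.05 | 38.25% / 33.25% | 1.24 | about 15% | 35.75% |
| A | 0.10 | 41.5% / 31.5% | 1.54 | about 44% | 36.5% |
| B | 0.05 | 38.25% / 35% | 1.15 | about 8% | 36.6% |
| B | 0.10 | 41.5% / 35% | 1.32 | about 21% | 38.25% |

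**Wider range of assumed accuracy.** Take observed proportion = p × sensitivity + (1 − p)(1 − specificity), with p from 10% to 50% and exposed against unexposed sites:
- Sensitivity 0.90 against 0.80, specificity 0.95 in both: OR 1.09 to 1.22; chance about 4% to 14%. The value below 5% arises because the approximation counts one tail only.
- Sensitivity 0.90 against 0.80, specificity 0.90 against 0.95: OR 1.35 to 1.54; chance 23% to 26%.
- Sensitivity 0.95 against 0.80, specificity 0.85 against 0.95: OR 1.65 to 2.09; chance 56% to 66%.
- Equal accuracy in both groups (0.85 and 0.95): OR 1.00, and the nominal 5% holds.

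**Effect on the primary endpoint.** With half the sites exposed, overall prevalence is the mean of the two groups. It shifts by 0.75 to 1.5 points in Model A, where the two errors partly cancel, and by about 1.6 to 3.25 points in Model B. The simple 95% half-width at 300 PIVCs is 1.96 × √(0.35 × 0.65/300) = 5.4 points.

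**The case against.** The strongest reply is that the study is openly observational and unblinded, that the associations are exploratory and examined only if appropriate (Section 6.1.3), and that safeguards exist: site-assessment training, a pilot site, written definitions, and monitoring with retraining. The GEE model is worded for patient characteristics, so dwell and infusate would enter mainly through the unadjusted tests. Figure 1 and the questionnaire itself are not visible here and might set an order. All of this limits the point. None of the visible safeguards, however, governs what the auditor knows when calling a borderline site.

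Three stronger readings are tempting and are not supported.
- A reader might infer that the chart must be read first because Section 3.3 names it first. That is word order in a list of sources. The gap is that no order is set.
- A reader might infer that complications found only in the chart enter the primary numerator. Sections 1.1 and 3.3 tie complications to observation, and the remark in 5.3 concerns serious or unanticipated events, not an endpoint rule. A clarifying sentence is worthwhile, but no error is shown.
- A reader might infer that the headline prevalence is seriously biased. In the illustration above, the shift stays inside the sampling half-width.

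That both tasks fall in one bedside visit is also an inference, from the single audit day and single form.

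**Conclusion.** The point stands as a cheap improvement to the assessment procedure. With no order set, chart knowledge can influence borderline calls and bias the associations tested in 6.2.4. On assumed differential error of 5% to 10% the spurious odds ratio is about 1.15 to 1.54; at the low end this matters little, and at the high end false positives run well above 5%. These values depend on the assumed prevalence, the even split, the direction of error and the neglect of clustering. The actual size cannot be derived from the documents. The likely effect on overall prevalence is small.

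For some items, dependence on infusate is part of the Appendix I definition: chemical phlebitis and extravasation both require knowing what was given. An association between these and infusate is partly built in, whatever the order of assessment.

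**What to change.** In Section 3.3, set the order for each patient rather than for each PIVC. With a per-PIVC order, the chart would already be open when a second site is scored.

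1. Check eligibility beforehand, including current transfer status, without opening the PIVC records.
2. At the bedside, record signs, complication presence, grades and quality issues for all of the patient's PIVCs.
3. Then abstract PIVC data from the chart. Use it to assign phlebitis etiology and to complete the items whose definitions depend on what was infused: extravasation against infiltration, the infusate element of infiltration grade 4, and blood reflux after a recent blood infusion. Do not otherwise revise the bedside calls.
4. State that only findings present at the bedside count for the endpoints.
5. State as a limitation that insertion labels and running infusions remain visible, so associations with dwell and infusate may still carry some bias.

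The cost is a few sentences in Section 3.3, a questionnaire layout that follows this order, and a slightly stricter workflow. No staff or visits are added.
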